### 3.3.3 Exclusion criteria

1. ALT, AST  $> 1.5$  fold upper limit of normal (ULN) at Visit 1;
2. Total bilirubin  $> 1.5$  fold ULN at Visit 1;
3. Patients with underlying *chronic* liver disease (Child Pugh A, B or C hepatic impairment);
4. Relevant airways obstruction [i.e. pre-bronchodilator FEV1/FVC  $< 0.70$  (i.e. 70%) at Visit 1];
5. History of myocardial infarction within 6 months of visit 1 or unstable angina within 1 month of Visit 1;
6. Bleeding Risk:
  - Known genetic predisposition to bleeding;
  - Patients who require fibrinolysis, full-dose therapeutic anticoagulation (e.g. vitamin K antagonists, direct thrombin inhibitors, heparin, hirudin etc.) or high dose antiplatelet therapy;
  - History of haemorrhagic central nervous system (CNS) event within 12 months prior to Visit 1;
  - History of haemoptysis or haematuria, active gastro-intestinal bleeding or ulcers and/or major injury or surgery within 3 months prior to Visit 1;
  - International normalised ratio (INR)  $> 2$  at Visit 1;
  - Prothrombin time (PT) and partial thromboplastin time (PTT)  $> 150\%$  of ULN at Visit 1;
7. Planned major surgery during the trial participation, including lung transplantation, major abdominal or major intestinal surgery;
8. History of thrombotic event (including stroke and transient ischemic attack) within 12 months of Visit 1;

9. Creatinine clearance < 30 mL/min calculated by Cockcroft–Gault formula at Visit 1 ([Appendix 10.2](#));
10. Treatment with nintedanib, pirfenidone, azathioprine, cyclophosphamide, cyclosporine, any other investigational drug, n-acetylcysteine, prednisone/prednisolone >15 mg daily or >30 mg every 2 days OR use of other systemic corticosteroids as well as any investigational drugs within 4 weeks of Visit 2;
11. Known hypersensitivity to nintedanib, peanut, soya or to any other components of the study medication;
12. Prior discontinuation of nintedanib treatment due to intolerability/ adverse events considered drug related;
13. A disease or condition which in the opinion of the investigator may interfere with testing procedures or put the patient at risk when participating in this trial;
14. Alcohol or drug abuse which in the opinion of the treating physician would interfere with the treatment and would affect patient's ability to participate in this trial;

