- (ii) marked haematological and other lab abnormalities or lead to significant concomitant therapy as identified by the Clinical Monitor/Investigator at a Blinded Report Planning Meeting.

An overall summary of adverse events will be presented. The frequency of patients with adverse events will be summarized by treatment, primary system organ class and preferred term. Separate tables will be provided for patients with other significant adverse events according to ICH E3 (11), for patients with adverse events occurring with an incidence in preferred term greater than 5% (in at least one treatment arm), for patients with adverse events leading to dose reduction, for patients with adverse events leading to treatment discontinuation, for patients with serious adverse events, for patients with related adverse events and for patient with significant (protocol-specified) AEs (as ticked in the AE page of the CRF).

The system organ classes will be sorted according to the standard sort order specified by EMA, preferred terms will be sorted by frequency (within system organ class).

Specific tables will be created in order to describe diarrhoea events:

- Display of the diarrhoea specific page of the CRF
- Summary of diarrhoea events including time to onset, number and duration of episodes

- Summary of diarrhoea adverse events including seriousness, clinical consequences (dose reduction, drug discontinuation or drug interruption) and outcome

Also, a Kaplan-Meier plot of time to first diarrhoea event will be drawn by treatment.

Similar summary tables including seriousness, clinical consequences and outcome will also be presented to describe the bleeding adverse events. Depending on the number of patients having such adverse events, summary tables including time to onset, number of episodes and duration together with Kaplan-Meier plot of time to first event may also be produced.

The following adverse event groupings have been defined outside the trial protocol:

Table 7.8.1: 1 Adverse events by system using aggregated terms

System	Safety Topic	Definition (selection criteria)
Gastrointestinal	Diarrhoea	PT Diarrhoea
	Nausea	PT Nausea
	Abdominal pain	HLT 'Gastrointestinal and abdominal pains (excl oral and throat)
	Vomiting	PT Vomiting
	Pancreatitis	SMQ Acute pancreatitis (narrow)
	Gastrointestinal perforation	SMQ Gastrointestinal perforation (narrow)
	Hepatobiliary	Drug-induced liver injury (DILI)

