Hepatic disorders (broad)		Table to show cumulative row for all 4 SMQs below, followed by a cumulative row for each subSMQ, followed by all PTs driving that subSMQ
Drug related hepatic disorders		SMQ Drug related hepatic disorders – comprehensive search (narrow) OR
Liver related investigations		SMQ Liver related investigations, signs and symptoms (broad) OR
Cholestasis and jaundice of hepatic origin		SMQ Cholestasis and jaundice of hepatic origin (narrow) OR
	Hepatitis non-infectious	SMQ Hepatitis, non-infectious (narrow)
	Hepatic failure	SMQ Hepatic failure, fibrosis and cirrhosis and other liver damage-related conditions (narrow)
Cardiovascular	Arterial thromboembolism	SMQ Embolic and thrombotic events, arterial (narrow)
	Myocardial infarction	SMQ Myocardial infarction (narrow)
	Stroke	PV Endpoint, see Section 9.2 for included Preferred Terms

Table 7.8.1: 1 (continued) Adverse events by system using aggregated terms

System	Safety Topic	Definition (selection criteria)
	MACE	Fatal events in SOC Cardiac Fatal events in SOC Vascular Any fatal or nonfatal events in SMQ Myocardial infarction (narrow) PTs Cardiac death, Sudden death, Sudden Cardiac death Any fatal or nonfatal Stroke events as defined in respective PV Endpoint
	Cardiac failure	SMQ Cardiac failure (narrow)
	QT prolongation	SMQ Torsade de pointes/QT prolongation (narrow)
	Venous thromboembolism	SMQ Embolic and thrombotic events, venous (narrow)
	Pulmonary embolism	PT Pulmonary embolism
	DVT	PT Deep vein thrombosis
	Hypertension	SMQ Hypertension (narrow)
Metabolic	Decreased appetite	PT Decreased appetite
	Weight decreased	PTs: Weight decreased, Abnormal loss of weight
Blood	Thrombocytopenia	PTs: Thrombocytopenia, Platelet count decreased, Immune thrombocytopenic purpura
	Haematopoietic thrombocytopenia	SMQ Haematopoietic thrombocytopenia (broad)
	Neutropenia	SMQ Agranulocytosis (narrow) OR SMQ Haematopoietic leukopenia (narrow)
	Bleeding	SMQ Haemorrhage terms (excl laboratory terms) (narrow) displayed in total and then according to categories: 
 • Gastrointestinal – oral • Gastrointestinal – upper • Gastrointestinal – lower • Gastrointestinal – nonspecific • Skin • Respiratory • CNS • Urogenital • Other
	GI bleeding – oral	
	GI bleeding – upper	
	GI bleeding – lower	
	GI bleeding – nonspecific	
	Skin bleeding	
	Respiratory bleeding	
	CNS bleeding	
	Urogenital bleeding	
	Other bleeding	
		See Section 9.3 for PT lists of the bleeding subcategories.

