Psychiatric	Depression	SMQ Depression (excl suicide and self-injury) (narrow)
	Suicide	SMQ Suicide/self-injury (narrow)
Renal	Renal failure	SMQ Acute renal failure (narrow)
	Proteinuria	SMQ Proteinuria (narrow)
	Glomerulonephritis	SMQ Chronic kidney disease (broad)
Cutaneous	Severe skin reactions	SMQ Severe cutaneous adverse reactions (narrow)
	Pruritus	PT Pruritus
	Rash	BIcMQ subsearch “Skin rash” (narrow)

Table 7.8.1: 1 (continued) Adverse events by system using aggregated terms

System	Safety Topic	Definition (selection criteria)
Liver laboratories	Hepatic enzyme increased	Following PTs: Alanine aminotransferase abnormal Alanine aminotransferase increased Aspartate aminotransferase abnormal Aspartate aminotransferase increased Hepatic enzyme abnormal Hepatic enzyme increased Hepatic function abnormal Hypertransaminasaemia Liver function test abnormal Transaminases abnormal Transaminases increased Blood alkaline phosphatase abnormal Blood alkaline phosphatase increased Gamma-glutamyltransferase abnormal Gamma-glutamyltransferase increased
	Hyperbilirubinaemia	Following PTs: Blood bilirubin abnormal Blood bilirubin increased Blood bilirubin unconjugated increased Hyperbilirubinaemia Icterus index increased Jaundice Jaundice hepatocellular Bilirubin conjugated abnormal Bilirubin conjugated increased
	Alanine aminotransferase increased	Following PTs: Alanine aminotransferase increased Alanine aminotransferase abnormal
	Aspartate aminotransferase increased	Following PTs: Aspartate aminotransferase increased Aspartate aminotransferase abnormal
	Gamma-glutamyl-transferase increased	Following PTs: Gamma-glutamyltransferase increased Gamma-glutamyltransferase abnormal
	Blood alkaline phosphatase increased	Following PTs: Blood alkaline phosphatase increased Blood alkaline phosphatase abnormal

These definitions are based on MedDRA version 21.0.

For analyses defined above, the blinded and open-label period will be analyzed separately. Additionally, a pooled analysis across both periods will be performed but including displays by randomized treatment.

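### In the SAP's aggregated adverse event table, the Glomerulonephritis row is selected by a broad chronic kidney disease search, so label and definition do not agree.

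*SAP*

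**What the plan says.** SAP section 7.8.1 introduces Table 7.8.1:1 with the statement "The following adverse event groupings have been defined outside the trial protocol". The protocol therefore gives no competing definition, and the table is the only one the two documents contain. Below the table the SAP adds "These definitions are based on MedDRA version 21.0".

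The Renal block has three topics:

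- Renal failure, selected by "SMQ Acute renal failure (narrow", narrow scope.
- Proteinuria, selected by "SMQ Proteinuria (narrow", narrow scope.
- "Glomerulonephritis", selected by "SMQ Chronic kidney disease (broad", broad scope.

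The third row has no footnote, preferred-term list or cross-reference. The SAP applies these groupings to the blinded period, to the open-label period and to both pooled, with displays by randomised treatment.

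**The concern.** A reader uses an aggregated safety table by its row labels. A count beside a named diagnosis is taken as the number of patients with that diagnosis. Here the label names one kind of kidney disease, while the rule collects a wider group of kidney disease at the less specific of the two scopes used in the table. A programmer who follows the rule exactly would place every captured event under the diagnosis in the label, whether or not the event is glomerular. The count and the treatment comparison in that row would then describe something other than what the row says. What is at stake is the accuracy of one descriptive row.

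**Working it through.** The documents state no figure on this point, so no arithmetic can be reproduced. The check is a comparison of text.

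**1. Is the pairing an artefact of a broken table?** Parts of this table are visibly displaced in the public text, notably the hepatobiliary rows. The Renal block does not look affected. The two rows above match their labels closely, and the Cutaneous rows below also pair sensibly. A shifted column would have upset those pairings too.

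**2. Is it the table's convention?** Three search criteria in the table use broad scope:

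| Row label | Search used | Does the label carry the name of the search? |
|---|---|---|
| Liver related investigations | liver investigations, signs and symptoms, broad | Yes, shortened |
| Haematopoietic thrombocytopenia | haematopoietic thrombocytopenia, broad | Yes |
| Glomerulonephritis | chronic kidney disease, broad | No |

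Only the third row puts a specific diagnosis on a broad search with a different name.

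**3. Does the SAP narrow the row elsewhere?** Where the SAP wants a particular set of terms, it says so. Stroke points to section 9.2, the bleeding subcategories point to section 9.3, and the liver laboratory rows list their preferred terms in the table. The glomerulonephritis row has no such pointer, so the absence of sections 9.2 and 9.3 from the public text does not explain it. For the broad hepatic grouping, the table also asks that each sub-search be "followed by all PTs driving that subSMQ". No such display is requested for the Renal rows.

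**4. Which events can reach the row?** Protocol section 5.3.7 treats abnormalities present before inclusion as baseline conditions, but it requires worsening of pre-existing conditions to be recorded as an adverse event. Protocol section 7.3.4 and SAP section 7.8.1 count as treatment-emergent the events that start under treatment or in the residual effect period, and earlier ones that deteriorate under treatment. New or worsening chronic kidney disease therefore has a documented route into the row. Stable disease at entry does not.

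**5. How large is the error?** Let K be the number of patients the search captures in a period, and G the number of those with at least one glomerular term. The row reports K under a label that means G, so the over-count is K − G. It lies between 0 (every captured patient has a glomerular term, or none is captured) and K (none has one). Neither K nor G can be derived, because the documents contain no term list for the search and no expected rate of kidney events.

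**The case against.** The strongest reply is that the table sets a short heading beside an explicit definition column, so the rule is disclosed, and that other headings are loose too. Renal failure uses an acute renal failure search, Pancreatitis uses an acute pancreatitis search, and Neutropenia includes a leukopenia search. This is fair as far as it goes, but those searches are all narrow in scope. It does not remove the mismatch here, where a specific diagnosis heads a broad search of another name.

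Three stronger readings are tempting, and the documents do not support them.

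- A reader might infer that the row will fill with chronic kidney disease because the protocol excludes only "Creatinine clearance < 30 mL/min calculated by" the Cockcroft–Gault formula (section 3.3.3) and so admits reduced renal function. Eligibility concerns prevalence at entry, and stable disease at entry is a baseline condition. The documents give no rate of new or worsening kidney events.
- A reader might infer that a true glomerulonephritis signal would be lost. SAP section 7.8.1 also tabulates adverse events by treatment, system organ class and preferred term, with separate tables for, among others, serious events, related events and events leading to discontinuation. A coded case would appear there under its own term.
- A reader might infer that adverse event tables in general are affected. Only this aggregated row is affected, once in each period displayed.

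The objection on consequence also stands. Adverse events are summarised without hypothesis testing, and glomerulonephritis is not among the adverse events of special interest in protocol section 5.3.6.1, which are gastrointestinal perforation and hepatic injury. A footnote lost from the public text cannot be wholly excluded, although nothing visible suggests one.

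**Conclusion.** The mismatch is real and confined to one row. Followed as written, the rule would report treatment-emergent events from a broad chronic kidney disease search as glomerulonephritis, in the blinded, open-label and pooled displays. No endpoint, test or trial conclusion depends on it, and the preferred-term tables allow a careful reader to see what the events were. They do not correct the aggregated row, whose label would still be wrong.

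The conclusion rests on two assumptions: that the Renal rows were read correctly from the table, and that a broad chronic kidney disease search includes non-glomerular terms. The second follows from the name and scope of the search, not from a term list in the documents. The documents do not show whether the label or the search reflects the intent. This is a minor correction that is worth making.

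**What to change.** Make the label and the search agree in SAP Table 7.8.1:1. The minimum is to keep the search and rename the row Chronic kidney disease (broad). If glomerulonephritis is the topic the sponsor wants, keep the label and replace the search with a listed set of preferred terms under the stated MedDRA version, following the SAP's own approach for stroke and bleeding. Either choice is sufficient, and a second row is not required.

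The cost is one edited table row, plus a short term list under the second option. No data collection, sample size or other analysis changes.

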7.8.2 Laboratory data

The analyses of laboratory data will be descriptive in nature and will be based on BI standards (see DM&SM: Display and Analysis of Laboratory Data) ([12](#)).

Please refer to Section 7.3.4 of the CTP. Please refer to [Section 5.4.4](#) for a definition of liver enzyme elevations.

Specific tables will be presented to describe liver enzyme elevations as defined in Section 5.4.4 by treatment group:

- Summary table of liver enzyme elevation including time to first onset and number of patients with liver enzyme elevation.
- Kaplan-Meier plot of time to first liver enzyme elevation (if sufficient number of events). No statistical test will be performed.
- Summary table of individual maximum liver enzyme and bilirubin elevations
- Plot of time course profile of liver enzyme for patients having liver enzyme and bilirubin elevation

7.8.3 Vital signs

Only descriptive statistics (by visit and change from baseline) are planned for this section of the report.

7.8.4 ECG

Not applicable.

7.8.5 Others

Not applicable.

10. HISTORY TABLE

Table 10: 1 History table

Version	Date (DD-MMM-YY)	Author	Sections changed	Brief description of change
Initial	23-SEP-16		None	This is the initial TSAP with necessary information for trial conduct
Final	19-JUL-18	(ext) /	All	This is the final TSAP
